3.3 Sample Size and Power Considerations

For the primary estimand, the sample size of 159 is expected to provide adequate power for the comparisons between MT-7117 and placebo for change from baseline in the average daily sunlight exposure time (minutes) to first prodromal symptom associated with sunlight exposure between 1 hour post sunrise and 1 hour pre-sunset at Week 26 based on the MT-7117-A01 study. The calculation of sample size assumes a 2-sided alpha level of 0.05 and a 20% dropout rate up to Week 26. The sample size of 42 completers per treatment group will provide 91% and 79% power to detect an effect size of 0.72 and 0.66 in the average daily time (minutes) to first prodromal symptom associated with sunlight exposure between 1 hour post sunrise and 1 hour pre-sunset at Week 26 (ie, an absolute treatment difference of 57 mins between MT-7117 [REDACTED] [REDACTED] vs placebo, 52 mins between MT-7117 [REDACTED] [REDACTED] vs placebo, and a standard deviation [SD] of 79.3 mins). The sample size of 42 completers was calculated by SAS simulation using the fixed sequence testing procedure in order to confirm the power affected by multiplicity adjustment in treatment comparison for primary endpoint. Taking into account for a 20% dropout rate up to Week 26, total sample size of 159 was calculated.

Due to the rapid enrollment rate in the last few months of the enrollment period after COVID-

19 restrictions were lifted in many countries, a total of 184 subjects were enrolled.

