7.2.2.3.5. Total time (hours) in duration of sunlight exposure between 1 hour post sunrise and 1 hour pre-sunset without prodromal symptoms.

The following is the procedure to calculate this endpoint.

1. Step 1 in section 7.2.2.3.1 will be applied.
2. The duration of sunlight exposure without prodromal symptoms and without phototoxic reactions in a day is calculated.
3. The sum of the above duration in each day during the 26-week DBT or DBE period (from Baseline date to Week 26 or from Week 26 to Week 52) is calculated as this endpoint.

The following endpoint is derived when applying the similar rule as above. Total time (hours) in duration of sunlight exposure between 1 hour post sunrise and 1 hour pre-sunset without prodromal symptom with the severity of greater than 0 on 11-point Likert scale and without phototoxic reactions (pain-free time hours)

The following endpoint is derived as pain-free days when applying the similar rule as above.

- Total number of days subject is exposed to sunlight for any duration between 1 hour post-sunrise and 1 hour pre-sunset without prodromal symptoms
- Total number of days subject is exposed to sunlight for any duration between 1 hour post-sunrise and 1 hour pre-sunset without prodromal symptom with the severity of greater than 0 on 11-point Likert scale and without phototoxic reactions (pain-free days)

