7.3 Analysis Visit Definitions

(1) eDiary data excluding in-clinic sunlight exposure test

The subjects will, in their diaries, record the sunlight exposure periods (start/end time), prodromal symptom periods, and pain periods. The subjects' sunlight exposure start and end times will be compared with their state capital cities sunrise and sunset times.

The analysis windows are defined in the table below. The nominal day for each week relative to the first dose day will be used. Day 1 is the first dose day.

Table 2 Analysis Visit Window for diary data

Analysis Visit	Nominal day	Analysis Visit Window for DBT analysis
Baseline*	Day 1	Day -14 to -1
Week 2	Day 15	Day 1 to 14
Week 4	Day 29	Day 15 to 28
Week 6	Day 43	Day 29 to 42
Week 8	Day 57	Day 43 to 56
Week 10	Day 71	Day 57 to 70
Week 12	Day 85	Day 71 to 84
Week 14	Day 99	Day 85 to 98
Week 16	Day 113	Day 99 to 112
Week 18	Day 127	Day 113 to 126
Week 20	Day 141	Day 127 to 140
Week 22	Day 155	Day 141 to 154
Week 24	Day 169	Day 155 to 168
Week 26 (DBT EOT)	Day 183	Day 169 to 182
Week 26 (DBE Baseline)	Day 183	Day 169 to 182
Week 28	Day 197	Day 183 to 196
Week 32	Day 225	Day 211 to 224
Week 39	Day 274	Day 260 to 273
Week 52 (DBE EOT)	Day 365	Day 351 to 364
EOT for DBT	Day 182 or discontinued during DBT	14 days before EOT for DBT
EOT for DBE	Day 365 or discontinued during DBE	14 days before EOT for DBE
Follow-up until Week 32 (DBT EOS)	6 weeks after EOT for DBT	the latest 1 to 14 days before Follow-up date not overlapping with treatment duration in DBT period
Follow-up until Week 58 (DBE EOS)	6 weeks after EOT for DBE	the latest 1 to 14 days before Follow-up date not overlapping with treatment duration in DBE period

During 26 weeks (DBT)	1 to 182	Day 1 to EOT for DBT period
During 26 weeks (DBE)	183 to 364	DBE Baseline to EOT for DBE period

* If subjects have at least 1 day between Day -1 and Day -14, the baseline value will be calculated from the data between Day -1 and Day -14. If subjects have no data of sunlight exposure between Day -1 and Day -14, then the Analysis Visit window will be expanded to Day -28 and the baseline value will be calculated from the data between Day -1 and Day -28.

(2) Non-diary data including in-clinic sunlight exposure test

Table 3 Analysis Visit Window for non-diary efficacy data

Analysis Visit	Nominal day	Analysis Visit Window
Baseline	First dose day	NA
Week 4	Day 29	Day 16 to 64
Week 12	Day 85	Day 72 to 119
Week 26 (DBT EOT)	Day 183	Day 134 to 202

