8.2 Efficacy Assessments

All efficacy endpoints will be analysed under primary estimand unless otherwise stated.

All data will be listed.

For DBT data analysis

All efficacy endpoints in Section 2.3.1, 2.3.2, and 2.3.3 will be summarized using descriptive statistics or using the number with percentage in the ITT1 population. All of the statistical model analyses stated in the below sections will be done in the ITT1 only for DBT data analysis only.

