The following endpoint will be listed and summarized by treatment and planned time point using descriptive statistics. The value of melanin density, change from baseline and % change from baseline in melanin density at each visit by skin segments and average of 6 skin segments will be plotted by treatment. The average of 6 skin segments for the melanin density and for the change from baseline in melanin density at each visit, will be analysed using MMRM model similar to the analyses for the primary endpoint. A subgroup analysis by region (North America, Europe, Japan, Australia), by Fitzpatrick scale test category (I-II or III-VI), by Melanin density at BL (\geq Median, $<$ Median) and by the [REDACTED] will be done.

- Change from baseline and % change from baseline in melanin density at each visit by skin segments. Average of 6 skin segments for the change from baseline and % change from baseline in melanin density at each visit.

The following endpoints will be analysed using either ANCOVA or ANOVA model. The ANCOVA model will include the treatment group, randomization strata as fixed factors together with continuous covariate terms for the corresponding baseline values except for the below total

time endpoints.

- Change from baseline for in-clinic sunlight exposure time (minutes) to the first prodromal symptoms or end of test, whichever comes first.
- Total time (hours) during the 26-week double-blind treatment period in duration of sunlight exposure between 1 hour post sunrise and 1 hour pre-sunset without prodromal symptoms.
- Total time (hours) during the 26-week double-blind treatment period in duration of sunlight exposure between 1 hour post sunrise and 1 hour pre-sunset without prodromal symptom with the severity of greater than 0 on 11-point Likert scale and without phototoxic reactions (pain-free time hours).
- Change from baseline in average daily duration of sunlight exposure regardless of time of day without prodromal symptoms assessed at Week 26.

The following endpoints will be summarized using descriptive statistics and Wilcoxon's rank sum test.

- Total number of days subject is exposed to sunlight for any duration without prodromal symptoms during 26-week double-blind treatment period.

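### Exploratory totals of symptom-free and pain-free hours and days are raw sums with two different end points and no adjustment for observed diary time

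*SAP*

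**What the plan says.** SAP 7.2.2.3.5 builds total symptom-free hours from daily values: "The sum of the above duration in each day during the 26-week DBT or DBE period". The parenthesis that follows runs the double-blind sum from the baseline date to Week 26. Pain-free hours and the two day counts follow a similar rule.

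Table 2 in SAP 7.3 gives another window. Its row for the 26-week double-blind totals reads "Day 1 to EOT for DBT period", and the same table sets end of treatment at Day 182 or at discontinuation during that period. The eDiary table in SAP 9.3 assigns this row to total time and number of days.

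For the hours, SAP 8.2.3 states "The following endpoints will be analysed using either ANCOVA or ANOVA model". The ANCOVA has treatment and randomization strata, but the baseline covariate is waived for the total-time endpoints. The day counts go to a Wilcoxon rank sum test. Neither method has a term for days observed. SAP 7.4, on missing data, has no rule for missing diary days in these totals.

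SAP 8.2 adds: "All efficacy endpoints will be analysed under primary estimand unless otherwise stated". Under SAP 2.2.1 that means treatment policy to the end of the double-blind period, whether or not study drug was stopped.

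**The concern.** A raw sum depends on how long a subject was observed as well as on benefit per day. A subject whose data end at Week 6 has 6/26 = 23% of a completer's opportunity to accumulate hours or days. A day with no diary record adds nothing. The SAP does not say so, but it follows from summing.

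The Table 2 window, if discontinuation there means stopping drug, also discards data that the estimand needs. Protocol 8.5 encourages subjects who stop drug to complete the remaining assessments, and protocol 10.7.1.1 has the diary kept daily through follow-up.

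At stake is the reading of endpoints close to the indication in the protocol synopsis, which is framed in terms of pain-free light exposure. A difference in total pain-free hours could reflect stopping and diary completion as much as effect on tolerance of light.

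**Working it through.** **The plan's own figures.** The documents give no power or expected value for these totals. The only sizing is for the primary endpoint (SAP 3.3): "The sample size of 42 completers per treatment group will provide 91% and 79% power to detect an effect size of 0.72 and 0.66", from differences of 57 and 52 minutes and an SD of 79.3. It reproduces:
- 57/79.3 = 0.72. Power = Φ(0.7188 × √21 − 1.96) = Φ(1.334) = 0.909, against 91%.
- 52/79.3 = 0.66. Power taken alone is 0.852. Simulating the fixed sequence, with both tests significant against a shared placebo arm, gives 0.790, against 79%.
- 42/0.80 = 52.5, rounded up to 53; 53 × 3 = 159.

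So the plan itself expects incomplete follow-up: "The calculation of sample size assumes a 2-sided alpha level of 0.05 and a 20% dropout rate up to Week 26". It gives no rate by arm.

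**The two windows.**

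| Subject | Sum to Week 26 (7.2.2.3.5) | Sum to end of treatment (Table 2) |
|---|---|---|
| Stops drug, keeps diary | Counted to Week 26 | Cut at discontinuation, if drug discontinuation is meant |
| Leaves the study | Cut at withdrawal | Cut at withdrawal |
| Misses diary days | Those days add nothing | Those days add nothing |

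The windows differ only in the first row. The last two rows lower the total under both.

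**Size of the shortfall.** Let d be the share of an arm whose data end early and f the mean fraction of the 182 days completed before that. The expected observed fraction is 1 − d(1 − f). With equal daily symptom-free time, the ratio of arm totals is the ratio of these fractions.

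Input for unequal stopping: protocol 5.2 reports discontinuation due to treatment-emergent adverse events of 14.3% in one Phase 2 active arm and 0% on placebo. It is used here as an assumption, as are the values of f.

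| Stopping, active vs placebo | f | Mean observed days | Active total vs placebo, no true effect | True +25% appears as |
|---|---|---|---|---|
| 14.3% vs 0% | 0.25 | 162.5 vs 182.0 | −10.7% | +11.6% |
| 14.3% vs 0% | 0.50 | 169.0 vs 182.0 | −7.2% | +16.1% |
| 14.3% vs 0% | 0.75 | 175.5 vs 182.0 | −3.6% | +20.5% |
| 20% vs 20% | 0.25 | 154.7 in both | 0 | +21.3% |
| 20% vs 20% | 0.50 | 163.8 in both | 0 | +22.5% |
| 20% vs 20% | 0.75 | 172.9 in both | 0 | +23.8% |

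The last column is in percent of a full-period placebo total. Example: 1 − 0.143 × 0.50 = 0.9285; 182 × 0.9285 = 169.0; 1.25 × 0.9285 − 1 = 0.161. Per observed day, the no-effect difference is 0 and the +25% stays +25% in every row.

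**Effect on the test.** This was simulated with 61 per arm (protocol 8.1), lognormal daily rates with an assumed between-subject CV of 0.4 or 0.8, stopping times uniform over the period, and a two-sided 5% t-test.

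| Stopping | CV | Rejection with no true effect | Power for true +25%: raw total | Power for true +25%: per-day rate |
|---|---|---|---|---|
| 14.3% vs 0% | 0.4 | 16% | 45% | 86% |
| 14.3% vs 0% | 0.8 | 8% | 17% | 34% |
| 20% vs 20% | 0.4 | 5% | 70% | 86% |
| 20% vs 20% | 0.8 | 5% | 29% | 34% |

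The per-day column is a best case: it gives early stoppers a rate as precise as a completer's.

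**The case against.** The strongest reply is that 7.2.2.3.5 itself says Week 26, protocol 6.2.3 defines these endpoints over the 26-week period, and SAP 8.2 puts them under treatment policy. On that reading off-drug diary time counts and only withdrawal and missing days remain. Table 2 also does not say whether discontinuation means of drug or of study. This stands in part. A reader might infer that the SAP definitely discards off-drug data; the documents show two unreconciled windows, not a settled rule. Even so, 9.3 ties these totals to the Table 2 row, and the lack of adjustment holds under both windows.

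Second, the illustration rests on one arm's adverse-event discontinuations in a 16-week study, treated as all-cause stopping with nothing contributed afterwards, and on zero placebo stopping. That is correct. A reader might infer an established bias between arms, or one that favours the drug. Neither is supported: no Phase 3 rates by arm are given, equal stopping produces no false difference, and under the Phase 2 pattern the shift runs against the active arm.

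Third, a 26-week total has no matching baseline total, and SAP 8.1.5 lists categorised baseline time to first symptom as a stratification factor. Leaving out a continuous covariate therefore costs precision and does not create bias. This stands.

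Fourth, SAP 7.2.2.3.3 already defines a per-day symptom-free duration. It covers one 14-day window at any time of day, so it complements the 26-week totals without replacing them.

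**Conclusion.** The point holds in a limited form. The SAP gives two windows for the same totals, one of them hard to square with its own estimand, and under either it compares raw sums without regard to observed diary time. The shift under no true effect is d(1 − f) when only one arm stops early: about 7% for 14.3% against 0% at mid-period, and 4% to 11% for f from 0.75 to 0.25. With equal 20% stopping it is zero, and the cost is dilution and lost power. All sizes depend on assumed stopping patterns and, for the test, assumed CVs.

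None of these totals is in the H1–H12 sequence, so the primary test and study-wise type I error are unaffected. A reader might extend the criticism to the pain-event count in H5 and H6, which is also a raw sum (SAP 7.2.2.3.4). The model text names no offset, but the SAS code is redacted, so no conclusion can be drawn there. A change is worth making because these endpoints lie close to the indication and the correction is cheap.

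**What to change.** 1. Reconcile 7.2.2.3.5 with Table 2: sum from Day 1 through Day 182, including diary data after drug discontinuation, as treatment policy requires.
2. Make the compared quantity hours per diary-observed day, and the proportion of observed days that are symptom-free or pain-free. Keep the planned ANCOVA and Wilcoxon methods, and keep raw totals as descriptive. An offset in log observed days belongs to a log-link model and does not fit these analyses.
3. Define an observed day as one with any diary entry, including a report of no exposure. The existing qualified-day rule, which requires non-zero exposure, would remove time spent indoors from the denominator. The diary questions in protocol Appendix 4 are redacted, so confirm that the diary separates no exposure from no entry.
4. Add baseline average daily time to first prodromal symptom as a covariate in the total-time ANCOVA, for precision.
5. Report observed diary days by arm and add a missing-data sensitivity analysis, because a per-day rate assumes that unobserved days resemble observed ones.

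The cost is SAP wording and minor code, with no new data. If Week 26 results are already unblinded, label these analyses as supplementary.

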7.2.2.4 PGIC

The following score will be assigned and used for each outcome.

1: Very Much Improved

- 2: Much Improved
- 3: Minimally Improved
- 4: No Change
- 5: Minimally Worse
- 6: Much Worse
- 7: Very Much Worse

7.2.2.5 PGIS

The following score will be assigned and used for each outcome.

- 1: None
- 2: Mild
- 3: Moderate
- 4: Severe
- 5: Very Severe

7.2.2.6 PROMIS-57

Raw score for each PROMIS domain will be calculated as follows:

- Physical function raw score = total of Question 1 (PRO001) – Question 8 (PRO008)
- Anxiety raw score = 48 (=6x8) – total of [Question 9 (PRO009) – Question 16 (PRO016)]
- Depression raw score = 48 (=6x8) – total of [Question 17 (PRO017) – Question 24 (PRO024)]
- Fatigue raw score = 48 (=6x8) – total of [Question 25 (PRO025) – Question 32 (PRO032)]
- Sleep Disturbance raw score = 48 (=6x8) – total of [Question 33 (PRO033) – Question 40 (PRO040)]
- Ability to Participate in Social Roles and Activities raw score = total of Question 41 (PRO041) – Question 48 (PRO048)
- Pain Interference = Pain Intensity = 0 (No pain) to 10 (Worst pain imaginable) numeric rating scale (Categorical)

Total raw score for PROMIS all domain will be calculated as follows:

- The mean of physical function raw score, anxiety raw score, depression raw score, fatigue raw score, sleep disturbance raw score, ability to participate raw score, pain interference rawscore.

If there is missing score data in an domain or total, the corresponding domain or total score will be missing.

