8.2.3 Exploratory Efficacy Endpoints

The following exploratory efficacy endpoints will be analysed using the similar model as specified for the primary analysis (MMRM) replacing the baseline average daily sunlight exposure time to first prodromal symptom as covariate with the corresponding covariates at baseline visit in the below bullets.

- Change from baseline in the average daily mean intensity on an 11-point Likert scale of the subject's prodromal symptoms over time during 26-week double-blind treatment period.
- Change from baseline in average daily duration (minutes) of prodromal symptoms during 26-week double-blind treatment period.

- Change from baseline in the average daily mean intensity of the subject's phototoxic reactions (associated with sun exposure) during 26-week double-blind treatment period on an 11-point Likert scale.
- Change from baseline in average daily duration (minutes) of phototoxic reactions (associated with sun exposure) during 26-week double-blind treatment period.
- Change from baseline for all total score and total score in each domain of, anxiety, depression, fatigue, sleep disturbance, ability to participate in social roles and activities, and pain interference in the PROMIS-57
- Change from baseline in PGIS at each visit.

The following endpoints will be analysed using the same negative binomial model with log link as specified for the secondary efficacy endpoint.

- Total number of sunlight-induced pain events defined as phototoxic events during 26-week double-blind treatment.
- Total number of sunlight-induced non-prodrome, phototoxic reactions during 26-week double-blind treatment.

The following endpoint will be analysed using the same logistic regression model as specified for the secondary efficacy endpoint.

- The percentage of subjects who are responders at Week 26 based on PGIC (Very Much Improved or Much Improved).

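### As printed, the exploratory PROMIS-57 total averages in a 0-10 pain rating that is not reversed, so pain relief probably lowers a total meant to rise with benefit

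*SAP*

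**What the plan says.** SAP 7.2.2.6 scores the questionnaire as follows.

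- Physical function (Questions 1-8) and social roles (Questions 41-48) are plain sums.
- Anxiety, depression, fatigue and sleep disturbance are each 48 minus the sum of eight items.
- The pain line reads "Pain Interference = Pain Intensity = 0 (No pain) to 10 (Worst pain imaginable) numeric rating scale (Categorical". It has no question numbers and no subtraction.
- The total is the unweighted mean of the seven scores, ending with "sleep disturbance raw score, ability to participate raw score, pain interference rawscore".
- On incomplete forms: "If there is missing score data in an domain or total, the corresponding domain or total score will be missing". No prorating or minimum number of items is given.

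SAP 8.2.3 fits an MMRM to "Change from baseline for all total score and total score in each domain of, anxiety, depression, fatigue" and the remaining domains, including pain interference. SAP 2.3.3 lists the total as exploratory, and it is absent from H1-H12 in SAP 8.2.1. Protocol 10.7.2.4 describes seven domains of eight questions each and says the effect on quality of life will be judged on the total and on each domain.

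**The concern.** Subtracting four symptom domains from 48 while leaving two function domains alone makes sense as a step to point all scores the same way. Pain is the one symptom score that does not get this step. It is then averaged with equal weight beside scores on a much wider range.

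At stake is the interpretation of a summary quality-of-life score in a disease whose main symptom is painful photosensitivity. A drug that relieves pain and improves the other domains would have part of its effect subtracted from its own total. Quality of life is a secondary objective, the extension reports the total again (SAP 2.3.4), and SAP section 1 says its statistical details override the protocol, so this derivation governs.

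A smaller matter sits in the same section. The raw scores are sums with no allowance for gaps, so one unanswered item makes a domain score missing. That includes physical function, which is tested in H11 and H12.

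**Working it through.** **Inputs.** The scoring rules come from SAP 7.2.2.6 and the eight items per domain from Protocol 10.7.2.4. Item codes are not visible because Protocol Appendix 5 is redacted. The item skip rate is not in the documents.

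**1. The plan's own constant.** Reversing eight items coded 1 to 5 gives 8 x (1 + 5) = 48, which matches the printed 48 (6 x 8). Each eight-item score therefore runs from 8 to 40, a span of 32. Pain spans 10.

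**2. Direction.** Assume symptom items rise with symptoms and function items rise with function. Then 48 minus a symptom sum rises as symptoms ease, and the two function sums rise as function improves, so all six read higher as better. Pain reads higher as worse.

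**3. Effect on the total.** Total = (sum of six domain scores + pain) / 7.

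- Best score in all six domains, no pain: (6 x 40 + 0) / 7 = 34.29.
- The same patient with worst pain: (6 x 40 + 10) / 7 = 35.71, the highest total possible.
- Each 1-point fall in pain changes the total by -1/7 = -0.14; with pain reversed it would be +0.14.

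**4. Share of benefit cancelled.** Let S be the summed gain in the six domains and d the fall in pain. The printed change is (S - d)/7 and the aligned change is (S + d)/7. The share lost is 2d/(S + d).

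| Pattern of improvement | S | d | As printed | Pain reversed | Share lost |
|---|---|---|---|---|---|
| Every component by 30% of its range | 6 x 9.6 = 57.6 | 3 | 7.80 | 8.66 | 10% |
| Every component by 3 raw points | 18 | 3 | 2.14 | 3.00 | 29% |
| Pain by 3, each other domain by 1 | 6 | 3 | 0.43 | 1.29 | 67% |

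**5. Pain interference.** The printed formulas use Questions 1-48 plus one pain rating. Protocol 10.7.2.4 implies eight pain-interference items. As printed, none of them is scored, although SAP 2.3.3 and 8.2.3 analyse that domain.

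**6. Missing items.** With independent skips at rate q per item, a domain score is missing at a visit with probability 1 - (1 - q)^8. For an assumed q of 0.5% this is 3.9%, and for 2% it is 14.9%. It is zero if the device forces completion.

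**The case against.** The strongest objection is that the pain line is malformed. Every other domain line carries question numbers and this one does not. The total refers to pain interference, while the secondary endpoint is pain intensity, and the SAP lists the two as separate endpoints. An eight-item formula may have been lost in PDF reading, with the 0-10 rating belonging to pain intensity alone. If a reversed pain-interference sum was lost, the direction fault in the total disappears. This cannot be settled from the text, so the source must be checked.

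Second, item coding is redacted. With pain unreversed, the total is coherent only if high scores mean worse health in all six other domains. High physical-function scores would then mean worse function, and H11/H12 would have to be read the other way round. If only the symptom codes run opposite to the assumption, the total is still incoherent, but in a different way, and reversing pain alone would not mend it. The objection therefore limits how firmly the fault can be stated, but the need to state directions stands.

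Third, a reader might infer that a confirmatory result is compromised by the direction fault. The documents do not support that: H7/H8 use pain intensity alone, H11/H12 use physical function alone, and domains are also analysed separately, so a pain benefit would still be visible. Nor do they support saying that most of the benefit vanishes. The 67% comes from a pattern in which pain moves 30% of its range and the others about 3% (1/32).

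Fourth, requiring complete items is a clear, prespecified rule. A reader might take it to drop subjects from H11/H12 wholesale. A missing post-baseline score removes only that visit, and the MMRM uses the subject's other visits; only a missing baseline score removes all change scores. The loss rate is an assumption, and clustered skipping would affect fewer forms.

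**Conclusion.** On the printed text, and if item codes rise with the named construct, the total mixes directions: pain relief lowers it by 0.14 per point while improvement elsewhere raises it. The cancellation is about 10% when every component improves by the same share of its range, and larger when pain moves relatively more. The fault is confined to an exploratory score, and no test in H1-H12 uses it. It depends on redacted coding and on a line that may be incomplete.

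Whatever the coding, two gaps stand in the printed section: no direction is stated for the six non-pain domains, and pain interference has no formula of its own.

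The missing-item rule is secondary. It does reach H11/H12, with an effect from nil (forced completion) to about 4-15% of domain scores per visit at an assumed 0.5-2% independent skip rate.

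**What to change.** In SAP 7.2.2.6:

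1. Check the pain line against the source file. Give pain interference its own formula with question numbers, separate from the 0-10 pain-intensity rating.
2. State the item coding and the direction of every domain.
3. Align the pain component with the rest and put all components on one range before averaging. If higher is better throughout, an 8-40 score becomes 100 x (score - 8)/32; if the 0-10 rating is kept in the total, it becomes 10 x (10 - rating). Alternatively, drop the total and report domains only.
4. State whether the device allows skipped items. If it does, score an eight-item domain when at least half its items are answered, as the mean of the answered items x 8, before any reversal. The half-items threshold is a proposal, not taken from the documents.

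The cost is SAP wording and a short derivation change, with no new data. The downside of prorating is that it treats the items of a domain as interchangeable. Dropping the total would depart from Protocol 10.7.2.4 and should be recorded in SAP section 10.
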